1 SYNOPSIS

N/A

2. SCHEDULE OF ACTIVITIES

Table 2.-1: Procedural Outline Screening		
Procedure	Screening Visit (up to 28 days prior to First Dose)^a	Notes
Eligibility Assessments		
Informed Consent	x	A participant is considered enrolled only when a protocol specific informed consent is signed.
Inclusion/Exclusion Criteria	x	
Medical History	x	Include any toxicities or allergy related to previous treatments.
Concomitant Medications	x	
Safety Assessments		
Physical Examination (PE)	x	If the screening PE is performed within 24 hours prior to dosing on Day 1 then a single exam may count as both the screening and pre-dose evaluation.
Physical Measurements	x	Includes height, weight, and BMI.
Vital Signs	x	Includes body temperature, respiratory rate, and seated blood pressure and heart rate. Blood pressure and heart rate should be measured after the participant has been resting quietly for at least 5 minutes.
Electrocardiogram (ECGs)	x	ECGs should be recorded after the participant has been supine for at least 5 minutes.
Laboratory Tests		
Drug Screen (urine or saliva)	x	
Alcohol Screen	x	Breathalyzer
Clinical Labs	x	Chemistry, CBC, Coagulation and urine dipstick for blood (if participant is able to produce urine).
Serology	x	HIV
Pregnancy test	x	WOCBP only. See Section 9.4.4 .
Stool sample for occult blood	x	Subjects may bring sample to the unit on or prior to D1.
Adverse Event Reporting		
Monitor for Serious Adverse Events	x	All SAEs must be collected from the date of participant's written consent until 30 days post discontinuation of dosing or participant's participation in the study if the last scheduled visit occurs at a later time.

^a Screening and Day -1 to -3 activities can be combined if performed on the same day

--

Clinical Protocol
BMS-986177

CV010010
FXIa

Table 2.-2: Procedural Outline Treatment

Procedure	D -1 to -3	D 1	D5	D8	D12	D13 to D15 /Study Discharge ^a	Notes
Safety Assessments							
Physical Examination (PE)	x						
Targeted PE		x	x	x	x	x	Targeted physical based on subject complaint.
Concomitant Medications	x	x	x	x	x	x	
Physical Measurements	x	x	x	x	x		Weight only. Collect prior to Day 1 visit and collect pre and post dialysis (SoC can be used).
Vital Signs	x	x	x	x	x	x	Includes body temperature, respiratory rate, seated blood pressure (BP), and heart rate (HR) on Day -1 to -3 and for those that discontinue prematurely. BP and HR (pre-dose & 3h post HD for all treatments on Days 1, 5, 8, and 12, at 24h post-dose only when BMS-986177 is administered).
Electrocardiogram (ECGs)	x	x	x	x	x		BP and HR should be measured after the participant has been resting quietly for at least 5 minutes. ECGs should be performed prior to Day 1 and conducted 3-6 hours post dialysis. (See note in screening procedures, Section 2)
Laboratory Tests	x	x	x	x	x	x	Labs should be obtained prior to Day 1 and obtained 3-6 h post dialysis. (See note in screening procedures, Section 9.4.4.)
Stool, occult blood	x	x	x	x	x		Anytime 2-20 h post-HD. Can bring sample to next HD session.
Pregnancy Test	x					x	WOCBP only. See Section 9.4.4.
Urine dipstick		x	x	x	x		For blood if urine is produced by the participant.

Revised Protocol No.: 03
Date: 06-Sep-2017

11

583

Clinical Protocol
BMS-986177

CV010010
FXIa

Table 2.-2: Procedural Outline Treatment

Procedure	D -1 to -3	D 1	D5	D8	D12	D13 to D15 /Study Discharge ^a	Notes	
Drug Test (urine or saliva or plasma)	x						Obtain Pre-dose if possible; anytime up to 2-20 h post HD if possible.	
Alcohol screen		x	x	x	x		Breathalyzer; Pre-dose	
Adverse Event Reporting								
Monitor for Non-Serious Adverse Events		x	x	x	x	x	AE collection to begin 3 hours prior to dialysis start on Day 1 regardless of study drug administered	
Monitor for Serious Adverse Events	x	x	x	x	x	x	See note in screening procedures.	
Pharmacokinetic (PK) Assessments								
Serial Blood PK Sampling		x	x	x	x		See Section 9.5, PK only being collected on days when BMS-986177 is administered depending on randomization.	
Single PK Sampling		Obtained 24-72 hours after each dose						
Pharmacodynamic (PD) Assessments								
Serial Blood PD Sampling		x	x	x	x		See Section 9.6 and Table 9.6-1 (for BMS-986177 and enoxaparin) and Table 9.6-2 (for UFH).	
Single PD Sampling		Obtained 24-72 hours after each dose of BMS-986177 only.						Only after BMS-986177 dosing. See Section 9.6 and Table 9.6-1.
Biomarker Assessments								
D-dimer, F1,2 and exploratory plasma sample		x	x	x	x		See Section 9.8 and Table 9.8-1 and Table 9.8-2.	

Revised Protocol No.: 03
Date: 06-Sep-2017

Clinical Protocol
BMS-986177

CV010010
FXIa

Table 2.-2: Procedural Outline Treatment

Procedure	D -1 to -3	D 1	D5	D8	D12	D13 to D15 /Study Discharge ^a	Notes
FXI antigen		x					See Section 9.8 and Table 9.8-1 and Table 9.8-2.
Clotting assessment for dialysis filter, drip chamber; dialysis circuit pressure; number and volume of saline flushes; Kt/V, Time to hemostasis at puncture site		x	x	x	x		See Section 9.8 and Table 9.8-1 and Table 9.8-2. Clotting Assessment to be conducted by a blinded staff member.
Retain dialysis filter		x	x	x	x		See Section 9.8.
Whole Blood Collection for Analysis of DNA Variants in ADME-related Genes and thrombosis and hemostasis related genes		x					See Section 9.7. Only one sample required per subject for the study. Maybe obtained any time on or after randomization
Additional Research Sampling		x	x	x	x (24-72 h post dose D12)		Residual samples from biomarkers and PD blood. See Section 9.8.1.
Clinical Drug Supplies							
Randomize	x						Visit can be conducted with scheduled HD session.
Study Drug Administration		x	x	x	x		Administration of study drugs (i.e., BMS-986177, enoxaparin, and UFH) will be depending on the randomized sequence the subject is assigned to.

^a Visit can be performed between D13-15 based on last PK sample obtained between 24-72 hours post D12 dose. End of study procedures should be performed for subjects that discontinue prematurely.

In the event of multiple procedures are required at a single time point, the following is a list of procedures from highest priority to low:

Revised Protocol No.: 03
Date: 06-Sep-2017

--

Clinical Protocol
BMS-986177

CV010010
FXIa

- Safety
- Pharmacokinetic Sampling
- Pharmacodynamic Sampling
- Biomarker sampling

Revised Protocol No.: 03
Date: 06-Sep-2017

14

586

[REDACTED]

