- b) Inability to comply with prohibited/restricted treatments as listed in [Section 7.7](#)

3) Physical and Laboratory Test Findings

- a) Evidence of organ dysfunction or any clinically significant deviation in physical examination, vital signs, ECG or clinical laboratory determinations beyond what is consistent with their degree of renal dysfunction and other underlying conditions as determined by medical history, physical examination, ECG, and clinical laboratory determinations.
- b) Subjects with macro-hematuria and/or fecal occult blood detected during screening, baseline, or documented during other recent medical assessment, unless deemed not clinically significant by the Investigator.
- c) Subjects at screening with the following abnormal laboratory values upon repeat testing are excluded:
 - i) Hemoglobin <9 g/dL
 - ii) Hematocrit < 30%
 - iii) Platelet count < 80,000/mm³
 - iv) ALT or AST > ULN
 - v) Total bilirubin > 1.5X ULN
 - vi) aPTT or PT/INR > 1.2X ULN

Clinical Protocol
BMS-986177

CV010010
FXIa

- d) Positive urine or saliva or plasma screen for drugs of abuse with exception for prescription medications
- e) Positive blood screen for HIV-1 and HIV-2 antibody

4) Allergies and Adverse Drug Reaction

- a) History of any significant drug allergy (such as anaphylaxis or hepatotoxicity)

5) Other Exclusion Criteria

- a) Prisoners or participants who are involuntarily incarcerated. (Note: under certain specific circumstances a person who has been imprisoned may be included or permitted to continue as a participant. Strict conditions apply and Bristol-Myers Squibb approval is required.)
- b) Participants who are compulsorily detained for treatment of either a psychiatric or physical (eg, infectious disease) illness

Eligibility criteria for this study have been carefully considered to ensure the safety of the study participants and that the results of the study can be used. It is imperative that participants fully meet all eligibility criteria.

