9. STUDY ASSESSMENTS AND PROCEDURES

- Study procedures and timing are summarized in the Schedule of Activities.
- Protocol waivers or exemptions are not allowed.
- All immediate safety concerns must be discussed with the Sponsor immediately upon occurrence or awareness to determine if the participant should continue or discontinue treatment.
- Adherence to the study design requirements, including those specified in the Schedule of Activities, is essential and required for study conduct.
- All screening evaluations must be completed and reviewed to confirm that potential participants meet all eligibility criteria before randomization. The investigator will maintain a screening log to record details of all participants screened and to confirm eligibility or record reasons for screening failure, as applicable.
- Procedures conducted as part of the participant's routine clinical management (eg, blood count) and obtained before signing of informed consent may be utilized for screening or baseline purposes provided the procedure meets the protocol-defined criteria and has been performed within the timeframe defined in the Schedule of Activities.

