9.4.4 Clinical Safety Laboratory Assessments

Investigators must document their review of each laboratory safety report.
A local laboratory will perform the analyses and will provide reference ranges for these tests.

Results of clinical laboratory tests performed on Day -1 to -3 must be available prior to first dose of study drug.

Hematology	
Hemoglobin	
Hematocrit	
Total leukocyte count, including differential	
Platelet count	
Coagulation	
PT	
aPTT	
INR	
Serum Chemistry	
Aspartate aminotransferase (AST)	Total Protein
Alanine aminotransferase (ALT)	Albumin
Total bilirubin	Sodium
Direct bilirubin	Potassium
Alkaline phosphatase	Chloride
Lactate dehydrogenase (LDH)	Calcium
Creatinine	Phosphorus
Blood Urea Nitrogen (BUN)	Magnesium
Uric acid	Creatine kinase
Fasting glucose (if possible)	

Urine Dipstick
Blood (only if the participant is able to produce urine)
Serology
HIV-1 and -2 antibody (screening only)
Other Analyses
Test for drugs of abuse (urine or saliva or plasma)
Alcohol breathalyzer
Fecal occult blood (screening and after each treatment period if sample can be obtained)
Pregnancy test (urine or blood)- WOCBP only

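### The schedule lets the stool samples that decide exclusion 3b arrive after randomization, and possibly after the first study dose, contrary to Sections 9 and 9.4.4

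*Protocol*

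**What the plan says.** Six places in the protocol bear on this.

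- Section 6.2, exclusion 3b: "Subjects with macro-hematuria and/or fecal occult blood detected during screening, baseline, or documented during other recent medical assessment, unless deemed not clinically significant"; that judgement is left to the investigator.
- Table 2.-1, screening stool sample: "Subjects may bring sample to the unit on or prior to D1".
- Table 2.-2, stool row, marked at Day -1 to -3 and at Days 1, 5, 8 and 12, with one note for all five columns: "Anytime 2-20 h post-HD. Can bring sample to next HD session".
- Table 2.-2, randomization row, marked only at Day -1 to -3: "Visit can be conducted with scheduled HD session".
- Section 9: "All screening evaluations must be completed and reviewed to confirm that potential participants meet all eligibility criteria before randomization". The same list makes adherence to the Schedule of Activities mandatory and rules out waivers.
- Section 9.4.4: "Results of clinical laboratory tests performed on Day -1 to -3 must be available prior to first dose of study drug". Its test list has the entry "Fecal occult blood (screening and after each treatment period if sample can be obtained".

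**The concern.** Exclusion 3b can be applied only once a stool result exists. The investigator's option to judge a positive result unimportant also needs a result to judge. If the sample may be delivered on Day 1, eligibility on this criterion can still be open when the patient is randomized, and possibly when the first study treatment is given.

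The study compares anticoagulants, its primary objective is safety, and 3b is one of the criteria meant to keep out patients who may already be bleeding. A patient found ineligible at that stage has been randomized and perhaps treated. Sites are also left with two binding instructions that cannot both be followed when a sample comes late.

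**Working it through.** The plan states no figure on this point. The check sets the passages against each other and builds a timeline.

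**1. Screening sample against randomization.** Randomization is at Day -1 to -3. Delivery is allowed up to and including Day 1. A Day 1 delivery is therefore always after randomization and breaks the Section 9 rule. The note does not say pre-dose, although other notes in the schedule do (the alcohol screen, for example).

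**2. Which session is next for the Day -1 to -3 sample.** Protocol Figure 5.1-1 puts Day 1 on Monday or Tuesday and Day 5 on Friday or Saturday. Carried back one week, and with no Day 0, the last dialysis before Day 1 falls on Day -3. It is the only session in the Day -1 to -3 window, and the randomization visit may coincide with it. The session after it is Day 1.

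**3. When that sample is produced.** Assume both sessions start at the same clock time, and count hours from the start of dialysis on Day 1. The Day -3 session starts at -72 h.

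- Session of 3 h: ends at -72 + 3 = -69 h; collection window -69 + 2 = -67 h to -69 + 20 = -49 h.
- Session of 4 h: ends at -72 + 4 = -68 h; collection window -68 + 2 = -66 h to -68 + 20 = -48 h.

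The stool is produced about 48 to 67 h before the Day 1 session. If randomization takes place at the Day -3 session, that is already after randomization.

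**4. Dosing against delivery on Day 1** (dose times from Section 5.1). BMS-986177 and enoxaparin are given at -3 h, and UFH starts within 10 minutes before dialysis. A sample handed over at the session arrives after dosing has begun in all four sequences. Sequences 2, 3 and 4 open with BMS-986177 or enoxaparin, so there the dose is already about 3 h old; with 1:1:1:1 allocation (SAP Section 2.2) that is 3/4 × 32 = 24 patients. Sequence 1 opens with UFH. A sample handed over when the patient reaches the unit can still precede the dose.

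**5. Reach of Section 9.4.4.** Its results-before-dose rule covers tests performed on Day -1 to -3. It does not reach an earlier screening test whose sample comes in on Day 1. Its list names occult blood only at screening and after each treatment period, where obtainable, so the Day -1 to -3 sample marked in Table 2.-2 is missing from it. Whether the rule is meant to govern that sample is unclear.

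**The case against.** The strongest reply is that the protocol already has the controls. Section 9 forbids randomization before screening has been reviewed, Section 9.4.4 forbids dosing without the Day -1 to -3 results, and Section 6.2 insists that all criteria be met. On this reading the table notes only concern how a sample is delivered. That reduces the finding to a conflict of wording but does not remove it: Section 9 makes the schedule binding too, so a site that follows the notes can also claim compliance.

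Two further replies have weight. Patients take a meal and have pre-dose assessments at the facility, and may be admitted the night before, so a sample brought along could well be handed in before the dose. Arrival after the dose is therefore possible, not expected. The 2-20 h note may also have been written for treatment days only, but its row includes Day -1 to -3 and gives no other instruction.

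A reader might infer more than the documents support:

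- *That no pre-treatment stool result would exist.* Late delivery does not make a specimen post-treatment. The Day -3 specimen is produced at least 48 - 3 = 45 h before the earliest dose, and SAP Section 7.1 defines baseline by collection time.
- *That the patient would meet an anticoagulant for the first time.* Section 7.7.1 allows heparin for routine dialysis, so the event at issue is the first study treatment dose.
- *That the crossover would be materially depleted.* Section 7.2 provides for replacement, with a restriction only for discontinuations due to adverse events, and Section 5.2 takes 32 patients to obtain 24 completers, a margin of 8.
- *That a count of affected patients can be given.* No positivity rate is stated, a second stool sample is scheduled before treatment, and a positive result may be judged not clinically significant.

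**Conclusion.** The contradiction stands. Delivery of the screening sample on Day 1 conflicts with Section 9. Delivery of the Day -1 to -3 sample at the next session conflicts with Section 9.4.4 if that rule covers stool tests, which its own test list leaves uncertain. The consequence is limited but concerns safety: a patient can be randomized, and possibly receive the first study treatment, before the result for a bleeding-risk exclusion has been read.

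The size can be given only as timing: always after randomization for a Day 1 delivery, and after the start of dosing only if the sample is handed over at the session. This rests on the Friday/Monday or Saturday/Tuesday dialysis pattern also holding in the week before Day 1. No effect on the planned analyses is shown. The change is worth making because it is cheap and the criterion protects patients.

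**What to change.** Reconcile the passages in an amendment.

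1. Table 2.-1: bring the stool note into line with Section 9, so that the screening result used for 3b is reviewed before randomization.
2. Table 2.-2: limit the next-session allowance to the Day 1, 5, 8 and 12 samples. For Day -1 to -3, either apply the Section 9.4.4 rule explicitly or state that the reviewed screening sample serves as baseline.
3. Section 9.4.4: make the occult blood entry agree with the columns marked in Table 2.-2, and state how its condition on obtaining a sample applies at screening.

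No new test is needed. The cost is that some patients are randomized later within the 28-day screening window. Once the result is required before randomization, a patient who cannot produce a sample needs a stated handling rule, which the sponsor has to decide.

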In summary, the overall safety profile of BMS-986177 in non-clinical and clinical studies supports further evaluation of the safety, tolerability, PK profile, and pharmacodynamic (PD) responses in ESRD patients undergoing HD. While the adverse effects observed in nonclinical studies at high multiple of exposure were not observed in healthy volunteers, these signals (LFTs) will be monitored in the setting of the current clinical study. All patients will be informed of the potential risks prior to enrollment in the study

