5. STUDY DESIGN

5.1 Overall Design

This study is a multicenter, cross-over, randomized, open-label trial with blinded endpoint assessment investigating safety and tolerability of single oral doses of BMS-986177 in patients with ESRD undergoing chronic stable HD three times per week. Secondary objectives are to assess BMS-986177 pharmacokinetics and hemodialysis success defined as completion of hemodialysis without premature interruption of the procedure due to complete clotting of the dialytic circuit and/or filter.

Study treatments will be administered on the first and last HD day of the week (either Monday and Friday, or Tuesday and Saturday, depending on the patients HD schedule), for a total of 4 treatment days (2 doses of BMS-986177, 1 dose of UFH, 1 dose of Enoxaparin).

The 2nd HD day of the week is not a study treatment day; on that day, study patients will undergo dialysis with standard of care, as per their schedule, and no study activities will be performed on those days.

Screening for inclusion in the study will be performed up to 28 days before the first study visit. After screening and meeting eligibility as per inclusion and exclusion criteria, patients will be randomized to 1 of following 4 sequences that will be conducted in parallel.

Sequence No.	Period			
	1	2	3	4
1	UFH	BMS dose 1 (BMS-986177 100 mg)	BMS dose 2 (BMS-986177 300 mg)	Enoxaparin
2	BMS dose 1 (BMS-986177 100 mg)	Enoxaparin	UFH	BMS dose 2 (BMS-986177 300 mg)
3	BMS dose 2 (BMS-986177 300 mg)	UFH	Enoxaparin	BMS dose 1 (BMS-986177 100 mg)
4	Enoxaparin	BMS dose 2 (BMS-986177 300 mg)	BMS dose 1 (BMS-986177 100 mg)	UFH

Note: Per amendment/revised protocol 01, the BMS-986177 doses will be 100 mg (BMS dose 1) and 300 mg (BMS dose 2).

Clinical Protocol
BMS-986177

CV010010
FXIa

Study patients will be admitted to the study facility the same day of HD treatment day or the night before. Assessment of vital signs and clinical biochemistry will be performed pre-dose.

Study treatments will be administered:

- BMS-986177: one single oral dose 3 hours prior beginning the HD session
- UFH: I.V. infusion to start within 10 minutes prior beginning the HD session. The dosage and duration of UFH use are at the discretion of the physicians and are per their institutional practice.
- Enoxaparin: one single dose (40 mg) by subcutaneous injection 3 hours prior beginning the HD session

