**Table 2.1-1 Randomization Scheme**

Sequence No.	Period			
	1	2	3	4
1	UFH	BMS dose 1 (BMS-986177 100 mg)	BMS dose 2 (BMS-986177 300 mg)	Enoxaparin
2	BMS dose 1 (BMS-986177 100 mg)	Enoxaparin	UFH	BMS dose 2 (BMS-986177 300 mg)
3	BMS dose 2 (BMS-986177 300 mg)	UFH	Enoxaparin	BMS dose 1 (BMS-986177 100 mg)
4	Enoxaparin	BMS dose 2 (BMS-986177 300 mg)	BMS dose 1 (BMS-986177 100 mg)	UFH

Study patients will be admitted to the study facility the same day of HD treatment day or the night before. Assessment of vital signs and clinical biochemistry will be performed prior to dosing.

The following study treatments will be administered:

- BMS-986177: 1 single oral dose 3 hours prior to beginning the HD session
- UFH: intravenous infusion to start within 10 minutes prior to beginning the HD session. The dosage and duration of UFH use are at the discretion of the physician and are per their institutional practice
- Enoxaparin: 1 single dose (40 mg) by subcutaneous injection 3 hours prior to beginning the HD session

The HD session will last approximately 4 hours. However, the duration could range from 3 to 4 hours but should be consistent on the days when study treatment is administered. After the HD, patients will remain in the study facility for at least:

- Approximately 3 hours post HD on UFH and enoxaparin treatment days
- Approximately 24 hours post dose on BMS-986177 days

Site staff members blinded to treatment will perform an assessment of clot formation according to criteria set forth in the Clot Formation Assessment Manual which will be provided to the site in a separate document.

Physical examinations (PEs), vital sign measurements, 12-lead electrocardiograms (ECG), and clinical laboratory evaluations will be performed at selected times throughout the dosing interval. Participants will be closely monitored for adverse events (AEs) throughout the study. Blood

samples will be collected for up to 72 hours after study treatment administration for PK analysis and PD analysis. Approximately 365 mL of blood will be drawn from each participant during the study.

The study design schematic is presented in Figure 2.1-1.

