#### **7.6.4 Clinical Laboratory Evaluations**

The results of all protocol-specified clinical laboratory tests will be listed by patient for the safety population. Laboratory measurements and corresponding change from baseline values will be summarized by treatment and scheduled nominal visit for each laboratory test.

Laboratory evaluations will be reported both in conventional units and in SI units.

Laboratory results will be classified as markedly abnormal based on sponsor defined criteria. The criteria used for classifying laboratory test results as markedly abnormal will be listed. Laboratory results for patients with any marked laboratory abnormality (scheduled and unscheduled) will be listed. This listing will include all observations for the specific laboratory test and patient, not only the marked laboratory abnormality measurements. The frequency of patients with any marked laboratory abnormality, based on pre-specified criteria, will be presented.

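### The safety chemistry and haematology panel is scheduled 24-72 h after dosing only in Period 4, and the SAP's period rules place later results under the next treatment

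*Protocol*

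**What the plan says.** **When labs are drawn.** The laboratory row of Protocol Table 2.-2 covers D -1 to -3, the four treatment days and discharge, with the instruction: "Labs should be obtained prior to Day 1 and obtained 3-6 h post dialysis". On discharge timing, footnote a states: "Visit can be performed between D13-15 based on last PK sample obtained between 24-72 hours post D12 dose". For patients who stop early it adds: "End of study procedures should be performed for subjects that discontinue prematurely". Protocol 9.4 refers to the Schedule of Activities for the planned times of every safety assessment.

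**Pre-dose biochemistry.** Protocol 5.1, describing treatment days, says: "Assessment of vital signs and clinical biochemistry will be performed pre-dose". SAP 2.1 repeats it: "Assessment of vital signs and clinical biochemistry will be performed prior to dosing". Table 2.-2 shows no pre-dose laboratory sample on D5, D8 or D12.

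**What is drawn at 24-72 h.** A PK sample is taken after each dose of BMS-986177. The single PD sample is described as: "Obtained 24-72 hours after each dose of BMS-986177 only". Protocol 9.6 limits the BMS-986177 PD analytes to aPTT and FXIc.

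**How results are tabulated.** SAP 7.6.4 says: "Laboratory measurements and corresponding change from baseline values will be summarized by treatment and scheduled nominal visit for each laboratory test". SAP 6.1 and Table 6.1-1 define Periods 1-4 by calendar date, so each period begins on the date of its own dose. SAP 7.1 defines one baseline, the last result before the first dose of study treatment, and 7.6.4 sets no other for labs. By contrast, vital signs (7.6.6) and PD (7.8) have a baseline for each treatment. SAP 7.6 keeps unscheduled samples out of the summary tables.

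**Why labs matter here.** Clinical laboratory values are part of the primary endpoint (Protocol Table 4.-1). Of the liver findings in non-clinical studies, the safety summary in Protocol section 3 says: "these signals (LFTs) will be monitored in the setting of the current clinical study".

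**The concern.** On a BMS-986177 day the scheduled panel is drawn 9-13 h after the dose. A change that develops later can be seen only in a later sample. For doses in Periods 1-3, Table 2.-2 provides no further panel until after the next treatment has been given.

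There are two consequences. First, a late change on a primary safety measure is looked for, in the window the protocol already uses for PK and PD, after only a quarter of BMS-986177 doses. Second, when a late change is found on D5, D8 or D12, the SAP's rules count it under the treatment given that day and measure it from the pre-study baseline. Nothing in the table marks it as carried over. The by-treatment laboratory tables then mix early values for one treatment with late values for the one before.

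**Working it through.** **The plan's own figure.** Protocol 10.1 and SAP 5 give over 80% probability of at least one event of 5% incidence in 32 patients. 1 − 0.95^32 = 0.806, so the figure is reproduced. It assumes that all 32 patients are observed for the event.

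**Time of the scheduled panel.** Dose at 0 h and dialysis from 3 h (Protocol 5.1). Dialysis lasts 3-4 h, and labs follow 3-6 h later.
- 4 h session: 3 + 4 + 3 = 10 h to 3 + 4 + 6 = 13 h after dosing.
- 3 h session: 9 h to 12 h.

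**What follows each BMS-986177 dose.** Treatments are given on D1, D5, D8 and D12, so the gaps are 96, 72 and 96 h. The last column takes the next panel from Table 2.-2 alone, with a 4 h session (gap + 10 h to gap + 13 h).

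| Sequence | Period | Dose | Next treatment | Gap | Next panel |
|---|---|---|---|---|---|
| 1 | 2 | 100 mg | 300 mg | 72 h | 82-85 h |
| 1 | 3 | 300 mg | Enoxaparin | 96 h | 106-109 h |
| 2 | 1 | 100 mg | Enoxaparin | 96 h | 106-109 h |
| 2 | 4 | 300 mg | none | – | D13-15 |
| 3 | 1 | 300 mg | UFH | 96 h | 106-109 h |
| 3 | 4 | 100 mg | none | – | D13-15 |
| 4 | 2 | 300 mg | 100 mg | 72 h | 82-85 h |
| 4 | 3 | 100 mg | UFH | 96 h | 106-109 h |

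Six of 8 positions (75%) lie outside Period 4, and 3 of 4 at each dose level. With 32 patients, 8 per sequence, that is 6 × 8 = 48 of 64 doses. With 24 completers, 6 per sequence, it is 36 of 48. The next treatment is a heparin in 4 of the 6 positions and the other BMS-986177 dose in 2.

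**If Protocol 5.1 is followed.** Biochemistry on D5, D8 and D12 falls about 96, 72 and 96 h after the previous dose and before the next. Protocol 9.4.4 lists AST, ALT and bilirubin under serum chemistry, and haemoglobin and platelets under haematology. Pre-dose biochemistry would therefore cover the liver tests and leave haemoglobin and platelets unsampled between 3-6 h after dialysis and the next treatment.

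**Where the SAP puts such a result.** Take a D5 sample drawn before the D5 dose. By Table 6.1-1, Period 1 ends before the D5 date, so the sample belongs to Period 2. By 7.1 it is post-baseline. By 7.6.4 it is summarised by treatment and visit, hence under the Period 2 treatment, which has not yet been given. The SAP has no laboratory-specific rule that overrides this. The same applies to a D8 sample drawn before dosing, which Protocol 9.5 allows as the late sample for Period 2 (days 6-8).

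**Direction of the misplacement.** The four sequences contain each of the 12 ordered treatment pairs once. BMS-986177 is followed by a heparin in 4 pairs, and a heparin by BMS-986177 in 4. At 8 per sequence that is 32 exposures each way.

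**Detection, as an illustration.** Assume a delayed laboratory change of 5% incidence, visible only at 24-72 h, and equal sequences. The chance of at least one case is 1 − 0.95^n.

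| Setting | Late samples now | Chance now | Late samples with fix | Chance with fix |
|---|---|---|---|---|
| One dose level, 32 patients | 8 | 33.7% | 32 | 80.6% |
| One dose level, 24 completers | 6 | 26.5% | 24 | 70.8% |

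If the change occurs at both doses, the 16 Period 4 samples come from 16 different patients (sequences 2 and 3), giving 1 − 0.95^16 = 56.0%.

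**The case against.** Three stronger readings are tempting, and the documents do not support them.

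- **That a delayed liver-enzyme rise is always first seen after the next treatment.** Protocol 5.1 and SAP 2.1 both state pre-dose biochemistry. If it is drawn, liver tests are seen before the next dose. What remains is that the Schedule, which Protocol 9.4 makes the list of safety timepoints, omits the draw, and that haematology is not named in it.
- **That there is no laboratory sample at 24-72 h.** aPTT, which is also on the safety coagulation panel, is drawn then after every BMS-986177 dose. Early discontinuers receive end-of-study labs, at an unstated time after their last dose. The gap concerns chemistry and haematology.
- **That the plan makes BMS-986177 look safer.** Succession is balanced, so late heparin effects fall under BMS-986177 as often as the reverse. A bias in favour of BMS-986177 would need delayed changes from that drug alone, which the documents do not establish.

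There are also safeguards. SAP 7.6.4 lists every observation of the affected test for a patient with a marked abnormality, so the time course can be read patient by patient. Adverse events go to the last treatment given at onset (SAP 7.6.3). Stool blood is checked 2-20 h after dialysis. No hypothesis is formally tested. These reduce the harm, but they do not correct the summary tables.

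Finally, no figure in the documents shows that 9-13 h is too early and 24 h late enough. A panel at 24 h would come only 11-15 h after the existing one. This limits what the extra panel can promise. The attribution problem does not depend on it.

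**Conclusion.** The point holds as an ascertainment gap and an attribution defect, not as a demonstrated bias. By Table 2.-2, 75% of BMS-986177 doses (48 of 64 at 8 per sequence) have no scheduled chemistry or haematology panel at 24-72 h. Whether liver tests are seen before the next treatment depends on an unresolved difference between Table 2.-2 and Protocol 5.1/SAP 2.1. Haemoglobin and platelets have no scheduled sample in that interval on either reading.

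The date-based periods, single pre-study baseline and by-treatment summary place a D5, D8 or D12 result under the next treatment, even when it is pre-dose. This follows from reading SAP 6.1, 7.1 and 7.6.4 together; no single sentence says so.

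The detection figures (34% against 81% per dose level; 26% against 71% with 24 completers) are illustrative. They credit nothing to pre-dose biochemistry, and the first pair assumes no dropout. The change is worth making because it is cheap and concerns a primary endpoint.

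**What to change.** 1. In Table 2.-2, add chemistry and haematology to the 24-72 h PK/PD draw that already follows each BMS-986177 dose.
2. Reconcile Table 2.-2 with Protocol 5.1 and SAP 2.1 on whether labs are drawn before dosing on D5, D8 and D12, and which panels.
3. In SAP 7.6.4, assign laboratory results by collection date-time relative to dose. Pre-dose and 24-72 h results, including a D8 sample taken before dosing, then belong to the preceding treatment. Report a 24-72 h post-dose row.
4. Show the D13-15 labs in that row for the Period 4 treatment. State that late values and marked-abnormality counts are not compared with the heparin columns, because ascertainment is unequal.

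A change that persists past the next dose will still enter that treatment's post-dialysis value under the single baseline. The late row makes this visible but does not remove it.

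**Cost.** One or two extra tubes at an existing draw: two draws per patient in sequences 1 and 4, and one in sequences 2 and 3 (the other dose is covered at discharge), or 48 panels for 32 patients. The blood volume rises slightly above the stated 365 mL or so. No visit or venepuncture is added. The drawback is that late sampling becomes more frequent after BMS-986177 than after the heparins, which is why item 4 is needed.
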